9.8 Safety Monitoring

Safety monitoring will include careful assessment and appropriate reporting of adverse events (AEs). Medical monitoring will include contemporaneous assessment of serious adverse events. Refer to Section 10 for AE definitions and additional information.

The monitoring of Subject safety and data quality will follow the NINDS Guidelines for Data and Safety Monitoring in Clinical Trials. A Data and Safety Monitoring Board (DSMB) appointed by the NIH/NINDS will meet at six-month intervals (or as determined by the NINDS) to review partially unblinded study data provided by the study statistician. This committee will monitor rates of adverse events and endpoints in the trial and will monitor the performance of the trial. The frequency and format of DSMB meetings, reports, and guidelines will be agreed upon prior to study Subject enrollment.

An Independent Medical Monitor (IMM) will be appointed to review all adverse events, in a blinded fashion, on a periodic basis. In addition, the IMM will review all events that meet the regulatory definition of a Serious Adverse Event, upon receipt of notification via the Electronic Data Capture (EDC) system.

FDA, Office of Human Research Protection (OHRP), and NeuroNEXT CIRB requirements for reporting AEs will be followed. Subjects will be monitored for AEs from the time they are randomized until 30 days following permanent discontinuation of study drug. At that point, all ongoing AEs will be followed to resolution or stabilization, whichever occurs first, but no new AEs will be recorded. The IMM/DSMB will review cumulative AEs; the frequency of this review will be determined by the IMM/DSMB.

For the purposes of this study, before randomization, only those adverse events, serious and non-serious, that in the opinion of the Investigator are deemed related to study procedures will be reported. After randomization, all adverse events will be reported.

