10 DEFINITIONS OF ADVERSE EVENTS, SUSPECTED ADVERSE DRUG REACTIONS & SERIOUS ADVERSE EVENTS

10.1 Adverse Event and Suspected Adverse Drug Reactions

An adverse event (AE) is any unfavorable and unintended sign (including a clinically significant abnormal laboratory finding, for example), symptom, or disease temporally associated with a study, use of a drug product or device whether or not considered related to the drug product or device.

Adverse drug reactions (ADR) are all noxious and unintended responses to a medicinal product related to any dose. The phrase "responses to a medicinal product" means that a causal relationship between a medicinal product and an adverse event is at least a reasonable possibility, i.e., the relationship cannot be ruled out. Therefore, a subset of AEs can be classified as suspected ADRs, if there is a causal relationship to the medicinal product.

Examples of adverse events include: new conditions, worsening of pre-existing conditions, clinically significant abnormal physical examination signs (i.e. skin rash, peripheral edema, etc), or clinically significant abnormal test results (i.e. lab values or vital signs), with the exception of outcome measure results, which are not being recorded as adverse events in this trial (they are being collected, but analyzed separately). Stable chronic conditions (i.e., diabetes, arthritis) that are present prior to the start of the study and do not worsen during the trial are NOT considered adverse events. Chronic conditions that occur more frequently (for intermittent conditions) or with greater severity would be considered as worsened and therefore would be recorded as adverse events.

Adverse events are generally detected in two ways:

Clinical → symptoms reported by the Subject or signs detected on examination.

Ancillary Tests → abnormalities of vital signs, laboratory tests, and other diagnostic procedures (other than the outcome measures: the results of which are not being captured as AEs).

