10.3.3 Recording of Adverse Events

All clinical adverse events are recorded in the Adverse Event (AE) Log in the Subject's study binder. The site should fill out the AE Log and enter the AE information into the online Adverse Event Reporting System within 5 working days of the site learning of a new AE or receiving an update on an existing AE.

Please Note: Serious Adverse Events (SAEs) must be reported to the NeuroNEXT Data Coordinating Center within 24 hours of the site learning of the SAE.

Entries on the AE Log (and into the online Adverse Event Reporting System) will include the following: AE term(s) and severity of the event, the date of onset, the date of resolution, relationship to investigational product, action taken, and primary outcome of event.

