3. SECONDARY ENDPOINT

The secondary endpoint for safety is defined as the proportion of study participants who experience any treatment-emergent (starting at or after the first dose of study medication) adverse event (AE) or serious adverse event (SAE). For the purposes of this study, a treatment emergent adverse event (AE) is any untoward medical occurrence associated with the use of a drug in humans, whether or not considered drug related. FDA, Office of Human Research Protection (OHRP) and NeuroNEXT CIRB requirements for reporting AEs will be followed. AEs are generally detected in two ways:

- Clinical → Symptoms reported by the study participant or signs detected on examination
- Ancillary Tests → Abnormalities of vital signs, laboratory tests, and other diagnostic procedures

If discernible at the time of completing the AE source documentation, a specific disease or syndrome rather than individual associated signs and symptoms should be identified by the Site Investigator and recorded in the AE documentation. However, if an observed or reported sign, symptom, or clinically significant laboratory anomaly is not considered by the Site Investigator to be a component of a specific disease or syndrome, then it should be recorded as a separate AE in the source documentation. Clinically significant laboratory abnormalities, such as those that require intervention, are identified as such by the Site Investigator.

Each clinical study site's Principal Investigator and research team (co-investigators, research nurse, and clinical trial coordinator) are responsible for identifying and reporting AEs through the NeuroNEXT Online Adverse Event Reporting System. The AE definitions and reporting procedures used for this study comply with all applicable U. S. Food and Drug Administration (FDA) regulations and International Conference on Harmonization (ICH) guidelines. The Site Investigator will carefully monitor each study participant throughout the study for possible AEs. All AEs will be documented on CRFs designed specifically for this purpose. It is important to report all AEs, especially those that result in permanent discontinuation of the investigational product, whether serious or non-serious. Local site investigators are also required to fulfill all reporting requirements of their local institutions.

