Study participants who sign consent and receive investigational treatment will be monitored for AEs from the time they sign consent through week 12 or the end of their study participation. This study utilized the CTCAE version 4.03 coding system for AE recording. AEs reported using CTCAE will be recoded into MedDRA terms by the DCC.

At each visit, the participant will be asked "Have you had any problems or symptoms since your last visit?" in order to determine the occurrence of AEs. If the study participant reports an AE, the Investigator will determine:

- Type of event
- Date of onset and resolution (duration)
- Severity (mild, moderate, severe, life-threatening, results in death)
- Seriousness (does the AE meet the definition of an SAE)
- Causality, relation to investigational product and disease
- Action taken regarding investigational product
- Outcome

All clinical AEs are recorded in the AE data entry template in the study participant's study binder. The sites should fill out the AE data entry template and enter the information into the Online Adverse Event Reporting System (AERS) within 5 working days / 7 calendar days of the site learning of a new AE or receiving an update on an existing AE. Entries in the AE data entry template will include the following:

- Name and severity of the AE
- Date of onset
- Date of resolution

- Relationship to study drug
- Action taken
- Primary outcome of event

The severity of all AEs will be graded according to CTCAE, version 4.03. Any AE not listed in the CTCAE will be graded as follows:

- Grade 1 – Mild: Transient or mild discomfort; No limitation in activity; No medical intervention/therapy required
- Grade 2 – Moderate: Mild to moderate limitation in activity; Some assistance may be needed; No or minimal medical intervention/therapy required
- Grade 3 – Severe: Marked limitation in activity, some assistance usually required; Medical intervention/therapy required; Hospitalizations possible
- Grade 4 – Potentially Life-Threatening: Extreme limitation in activity; Significant assistance required; Significant medical intervention/therapy required; Hospitalization or hospice care probable
- Grade 5 – Death: The AE results in death

The Site Investigator is initially responsible for classifying AEs as serious or non-serious. An AE is considered serious if it meets one or more of the following criteria:

- Results in death

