8. SECONDARY ANALYSIS

Secondary Objective: *The secondary objective is to evaluate the safety of SRX246.*

The safety objective will be met by conducting a non-inferiority test of the proportion of study participants with AEs or SAEs among the placebo group and each of the treatment groups (separate tests for placebo vs 120 mg and placebo vs 160 mg). The safety analysis will be conducted in a similar manner as the tolerability analysis. Each study participant will be classified as having experienced a treatment-emergent AE or SAE (event = "Yes") or not (event = "No"). Suppose the proportion of events in the placebo group is now denoted as π_{placebo} and the proportion of events in the 120 mg group is now $\pi_{120\text{mg}}$, with $\theta = \pi_{\text{placebo}} - \pi_{120\text{mg}}$. The same onesided CI will be used to test the same null hypothesis ($H_0: \theta \geq \delta$) with the same threshold ($\delta = 0.5$) as in the tolerability analysis. Each treatment group (120 mg, 160 mg) will be compared to the placebo group using $\alpha = 0.025$, meaning a $1 - \alpha = 0.975$ one-sided CI will be used for each test. Results will be summarized as shown in Table 3 below.

Table 3. Summary of Safety Analyses

	Placebo (N = XX)	120 mg (N = XX)	160 mg (N = XX)
Any AE	XX (XX%)	XX (XX%)	XX (XX%)
Any Treatment-Related AE	XX (XX%)	XX (XX%)	XX (XX%)
Any Serious AE	XX (XX%)	XX (XX%)	XX (XX%)
Early Drug Withdrawals (Any)	XX (XX%)	XX (XX%)	XX (XX%)
Early Drug Withdrawals (Due to AE)	XX (XX%)	XX (XX%)	XX (XX%)
Early Terminations (Any)	XX (XX%)	XX (XX%)	XX (XX%)
Early Terminations (Due to AE)	XX (XX%)	XX (XX%)	XX (XX%)
Deaths (Any)	XX (XX%)	XX (XX%)	XX (XX%)
Deaths (Due to AE)	XX (XX%)	XX (XX%)	XX (XX%)

In addition to an overall comparison, this hypothesis will be repeated for assessing the percentage of study participants having at least one treatment-emergent AE within each MedDRA system organ class (SOC). If there are specific differences within any specific SOC, then additional tests will compare differences across groups for specific MedDRA preferred terms in order to further explore the cause of the observed differences. Finally, the subset of treatment-related SAEs will be analyzed in the same manner described above.

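### The SAP's treatment-emergent rule looks only at the start date, so an adverse event recorded before the first dose that worsens on drug falls outside the safety endpoint

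*SAP*

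**What the plan says.** SAP section 3 defines the secondary endpoint as the proportion of participants with any "treatment-emergent (starting at or after the first dose of study medication) adverse event (AE) or serious adverse event (SAE". The next sentence describes a treatment-emergent event differently, as "any untoward medical occurrence associated with the use of a drug in humans, whether or not considered drug related", with no limit on onset. Neither sentence mentions worsening.

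SAP section 8 applies the term: "Each study participant will be classified as having experienced a treatment-emergent AE or SAE", yes or no. It repeats the test within each MedDRA system organ class, follows up at preferred-term level, and analyzes treatment-related serious events in the same way.

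On what an adverse event is, Protocol 10.1 says: "Examples of adverse events include: new conditions, worsening of pre-existing conditions". Chronic conditions that become more frequent or appear "with greater severity would be considered as worsened and therefore would be recorded as adverse events".

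On collection, SAP section 3 has participants "monitored for AEs from the time they sign consent through week 12 or the end of their study participation". Protocol 9.8 is narrower: "before randomization, only those adverse events, serious and non-serious, that in the opinion of the Investigator are deemed related to study procedures will be reported". On recording, Protocol 10.3.3 has sites enter information "within 5 working days of the site learning of a new AE or receiving an update on an existing AE", and SAP section 3 has an equivalent rule. Both entry lists show one severity, one onset date and one resolution date per event.

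**The concern.** The protocol's idea of harm is new or worse. The SAP's filter is new by date. An event can therefore be a recorded harm under the protocol and still not be treatment-emergent under the SAP. A Grade 1 event noted in screening that becomes Grade 3 or serious on drug is the plain example.

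The term drives every safety comparison in SAP section 8, so a literal programmer would drop such an event from the overall classification, its organ class and the treatment-related serious event subset. A second programmer, working from the wider sentence in the same paragraph, could keep it. The population makes the omission more noticeable: inclusion criterion 5 requires irritability or aggression at entry, and Protocol section 7 expects behavioral symptoms to appear as adverse events, so worsening of something already present is an ordinary form of harm in this trial.

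**Working it through.** The plan states no figure for this point, so the check is mainly a comparison of text, taking two kinds of event in turn.

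**Case A: a medical-history condition that worsens after first dose.**
1. Under Protocol 10.1 a stable chronic condition is not an adverse event, so it has no pre-dose event record.
2. When it worsens, the worsening is what gets recorded, and its natural onset is the date of worsening, after first dose. Dated that way, it meets the SAP rule.
3. If a site enters the date on which the condition first appeared, it fails. Neither document says which date to use.

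Result: normally counted, but dependent on an unstated convention.

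**Case B: an event recorded between consent and first dose that worsens afterwards.**
1. SAP section 3 opens collection at consent. Protocol 6.1 allows up to 30 days from screening to baseline, and Protocol 6.2 places randomization and then the first dose at the baseline visit. A pre-dose record is therefore possible.
2. The recording rules distinguish a new event from an update to an existing one. No section says that worsening opens a new record or resets the onset.
3. Read literally, the record keeps its pre-dose onset and fails the SAP rule, whatever grade it reaches.

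Result: left out.

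**How many are in case B.** Protocol 9.8 confines reports before randomization to procedure-related events. If sites followed the protocol, few pre-dose records exist. SAP section 3 does not repeat the limit, so the number depends on which window was used. Neither document gives a rate.

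**Effect on a displayed proportion.** Inputs: 36 planned per arm (SAP section 1); k = participants in an arm whose only event is a worsened pre-dose event (assumed, for illustration).

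Understatement = k / 36
- k = 1: 1/36 = 2.8 percentage points
- k = 2: 2/36 = 5.6 percentage points
- k = 4: 4/36 = 11.1 percentage points

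A participant with any other event starting at or after first dose is already a yes, so the any-event row moves only for those with none. Within one organ class or preferred term, the condition is only that the participant has no other qualifying event in that class or term. That is easier to meet, so those counts are more exposed, as is the treatment-related serious event count.

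**Direction.** In the displayed rates, omission lowers the apparent harm. In the formal test it does not simply help the drug. SAP section 8 sets θ = placebo proportion minus drug proportion and tests H0: θ ≥ 0.5. Dropping one drug-arm event in 36 raises the observed θ by 2.8 points, which makes rejection harder.

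**The case against.** The strongest reply is that the protocol already deals with most of this. Worsening is an adverse event in its own right, and Protocol section 7 gives worsening irritability and other behavioral symptoms their own characterization and outcome reporting. Entry irritability is an inclusion requirement, not a pre-dose adverse event. This largely stands. A reader might infer that any existing condition that worsens, irritability above all, drops out of the endpoint; the documents do not support that. What survives is that the dating convention is unstated.

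Second, Protocol 9.8 nearly empties the group of pre-dose records. This stands as a limit on size. It does not remove the gap, because SAP section 3 gives the wider window.

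Third, the update wording belongs to a reporting deadline and does not say that a worsening keeps the old onset. That is fair: the exclusion comes from a literal reading of silent text. The silence still leaves the programmer without a rule.

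Fourth, a reader might put a larger size on the problem. Suppose 10 to 30% of participants have something ongoing at first dose, and worsening runs at 10 to 20% on placebo against 30 to 50% on drug. The hidden difference is then 0.1 × (0.3 − 0.1) = 2 points up to 0.3 × (0.5 − 0.2) = 9 points. None of those rates is in the documents, the drug excess is assumed from the start, conditions covered by case A are mixed in, and the figures ignore participants who have another event. They should not be relied on.

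Fifth, Table 3 of SAP section 8 also shows withdrawals and terminations due to adverse events, and the safety monitor reviews all reported serious events as they arise. These displays limit the loss but do not correct the endpoint.

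**Conclusion.** The concern holds in a limited form. The SAP's definition rests on onset alone, sits beside a second definition without that limit, and does not match the protocol's concept of an adverse event. The clear omission is an event recorded between consent and first dose that increases in grade or becomes serious on drug. A worsened medical-history condition is at risk only through the missing dating rule.

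The group is probably small. Its size cannot be taken from the documents; the only firm figure is 2.8 percentage points per affected participant in an arm of 36, and only where that participant has no other qualifying event. The conclusion assumes that an update keeps the original onset date, which the text neither states nor excludes.

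A reader might also infer that the omission biases the formal safety test toward the drug. With the hypothesis as SAP section 8 writes it, losing drug-arm events works against rejection, so the under-counting favors the drug only in the descriptive rates. The primary tolerability endpoint is not affected.

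**What to change.** In SAP section 3, replace both descriptions with one definition: an adverse event is treatment-emergent if it starts at or after the first dose, or was present before it and increases in CTCAE grade or becomes serious at or after it. Then:

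- State that a worsening is dated at the worsening, for recorded events and medical-history conditions alike. The SAP describes enrollment largely in the past tense, so an instruction to sites may come too late. In that case derive the flag for recorded events from the update history; Protocol 10.3.5 says the reporting system keeps audit trails and updated data.
- Apply the same flag to the overall, organ class, preferred-term and serious event analyses.
- Reconcile the collection window in SAP section 3 with Protocol 9.8, and say which events recorded before first dose enter the database.

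A frequency criterion is better left out of the derived flag, because the entry lists carry no frequency field. A condition that becomes more frequent is already recordable under Protocol 10.1 and would count through its dated onset.

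The cost is a few sentences in the SAP and one derived variable. Adverse event percentages may rise slightly in all arms.

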4. ENROLLMENT & RANDOMIZATION

[figure not shown]
Following the screening phase, study participants who continue to meet entry criteria will be enrolled and randomly assigned in a 1:1 manner to one of three treatment groups: SRX246 120 mg, SRX246 160 mg, or matching placebo. A total of approximately 108 study participants will be randomized into the study. The treatment assignment for each participant will be assigned by a randomized code using randomization tables generated by the NeuroNEXT DCC using a block randomization scheme.

5. TABULATIONS

All study participants who provide informed consent will be accounted for in this study. The number of randomized participants and their study disposition will be reported overall, and by treatment group. The number of study participants who prematurely discontinued from the trial and the reason for discontinuation will be presented based on the categories on the Case Report Form (CRF). A CONSORT diagram summarizing the final status of all study participants will be provided in a flowchart similar to [Figure 1](#) below.

Additional summary reports will describe:

- Number of study participants consented, eligible, and randomized by site
- Reasons for ineligibility
 - A listing of all study participants with one or more inclusion/exclusion exceptions
- Completeness of study visits and case report forms
- Concomitant medications at beginning and end of study
 - Any medication recorded during the trial (from screening to end of study) is considered a concomitant medication. Concomitant medications will be coded using the World Health Organization Drug Dictionary (WHODrug)
 - Records of concomitant medications will be summarized separately for pre-dose (any medications with start date before baseline date) and end of study (any medication participant was on at the date of termination) using frequency counts for all medications at the Anatomical Therapeutic Chemical (ATC) class level 1 (Anatomical main group), and stratified by Pharmacological subgroup (level 3) for nervous system medications.
- Protocol deviations
 - A listing of all randomized study participants with one or more protocol deviations. The listing will include protocol violation category, and a description of the violation.
- Early drug withdrawals
- Early study terminations
- Study drug compliance
 - The number of expected doses of SRX246 or placebo received will be summarized as a continuous variable. Study participants will be deemed as “compliant” if the expected percentage of pills taken falls between 75% and 125% of expected pills.
 - A listing of all randomized study participants with their summary compliance information will also be provided.

Figure 1. CONSORT Diagram

Baseline demographics and clinical characteristics will also be summarized by treatment group (SRX246 120 mg vs. SRX246 160 mg vs. placebo) with respect to important demographic characteristics. Distribution of numeric and categorical variables will be tabulated by treatment group and overall. Numeric variables will be summarized by the mean, median, standard deviation, minimum, and maximum by treatment group and overall. Categorical variables will be tabulated by proportions or percentages. Variables that will be summarized include:

- Baseline Demographics
 - Gender
 - Race
 - Ethnicity
 - Age
 - Years of Education
- Baseline Clinical Characteristics
 - Cohen-Mansfield Aggression Inventory
 - Unified Huntington's Disease Rating Scale (UHDRS) Total Score
 - Irritability Scale – Participant
 - Irritability Scale – Study Partner
 - Total Functional Capacity
 - Irritability Frequency (UHDRS)
 - Irritability Severity (UHDRS)
 - Aggression Frequency (UHDRS)
 - Aggression Severity (UHDRS)
 - Suicidal Ideation
 - CAG Repeat Number

